#### 3. HYPOTHESES

- Asthma lung functional abnormalities can be quantified using 129Xe MRI over 2 years correlate significantly and strongly with dyspnea, pulmonary function and sputum measurements as well as indices of asthma quality of life and control. In addition, MRI VDP measured annually over a decade reflects significantly worse remodeling or will improve in response to therapy in those participants who opt for an annual visit.
- Xe MRI ventilation abnormalities are related to airway morphologies due to bronchospasm, airway structural remodeling and inflammation and these can be validated using CT and histology measurements of endobronchial biopsy samples;
- 129Xe MRI temporal functional maps will show significant correlations with functional images acquired 1 year later.
- Asthma underperceivers with poor control will exhibit significant baseline differences in fMRI BOLD contrast and DTI signal data compared to healthy volunteers.

DATE: November 15, 2024

- Quantitative fMRI data will be significantly correlated to pulmonary MRI data that quantifies abnormalities in lung function.
- Healthy volunteers and asthma underperceivers will show significant differences in BOLD contrast after undertaking a Methacholine challenge
- BOLD contrast will be significantly different between asthmatics and healthy volunteers post Methacholine challenge

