# 4.1.1. Methacholine Challenge

Methacholine Challenge will be performed for healthy volunteers and asthmatic participants in the Robarts Pulmonary Function Laboratory according to the American Thoracic Society Guidelines (ATS). After recording baseline FEV1, participants will inhale Methacholine solutions up to and including the concentration of Methacholine required to decrease FEV1 by 20% from baseline (PC20). After completion of dyspnea score and He or Xe at PC20, 400 μg of Salbutamol (4 puffs) will be administered followed by spirometry 20 minutes post-administration. Methacholine challenge will be performed at V1 baseline only.

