#### 4.1.2. MRI

Participants will be screened for contraindications by the MR technologist. Prior to being made comfortable on the scanner bed in the magnet, participants will be required to do a 16-second breath-hold test using a dose bag containing air similar to that used for xenon imaging. This maneuver ascertains their ability at that time to undergo administration of Xe gas and a 16-second breath-hold for the MR study. They will be placed in the 3T MR scanner with one of three Xe chest coils fitted over their torso and chest. Hearing protection will be provided to each participant to muffle the noise produced by the gradient RF coils. A pulse oximeter lead will be attached to all of the participants to monitor their heart rate and oxygen saturation. MRI will be performed for up to a period of 30 minutes. All participants will have supplemental oxygen provided via nasal cannula at a flow-rate of 2 liters per minute during the scanning process.

Once comfortable on the MRI scanner table, participants will undergo 1 MRI session containing acquisition of several images as follows:

Proton (H) imaging – participants will inhale a 1 litre gas mixture containing medical grade nitrogen (N2). This is performed in order to match breath hold volumes and anatomy with Xe images. Breath hold will be up to 16 seconds.

Static ventilation imaging – participants will inhale a 1 litre gas mixture containing Xe and or He (5 ml/kg body weight) mixed with helium-4 (He) from a 1 litre bag. Breathhold will be up to 16 seconds.

Diffusion-weighted imaging – participants will inhale a 1 litre gas mixture containing Xe and or He (5 ml/kg body weight) mixed with He from a 1 litre bag. Breath-hold will be up to 16 seconds.

Dissolved phase imaging – participants will inhale a 1 litre gas mixture containing Xe mixed with He from a 1 litre bag. Breath-hold will be up to 16 seconds.

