Logs and records of Xe and He gas exposure will be maintained for every participant in this study. Adverse experiences and pulse oximetry measurements during MRI will be recorded. If oxygen saturation falls to <80% continuously for ≥15 seconds, scanning will be discontinued, and the patient will be provided supplemental oxygen as necessary until oxygen saturation recovers to the patient's baseline value. This patient will then be discontinued from the study.

Participants undergoing resting state fMRI (healthy volunteers and the subset of asthmatic participants identified as underperceivers) will also be placed in the 3T MR scanner with a 32-channel brain coil fitted around their head. Hearing protection will be provided to each participant to muffle the noise produced by the gradient RF coils. A pulse

Protocol ROB0037, Robarts Research Institute Version 16

DATE: November 15, 2024

oximeter lead will be attached to all of the participants to monitor their heart rate and oxygen saturation. MRI will be performed for up to a period of 20 minutes. All participants will have supplemental oxygen provided via nasal cannula at a flow-rate of 2 liters per minute during the scanning process. Participants will undergo fMRI on two occasions during the first visit, each containing acquisition of an anatomical image, a BOLD signal image, and a diffusion tensor image. The sessions will be performed before and after the methacholine challenge for baseline and induced asthma attack or dyspnea conditions, respectively. Outlined in the table below are the appropriate pulse sequences designed for resting state fMR image acquisition:

Brain fMRI and lung MRI using Xe and/or He will be performed within five minutes of each other at both baseline and post-methacholine, and the order in which they are performed will be randomized for each participant and remain the same for both time points.

# Protocol ROB0037, Robarts Research Institute Version 16

DATE: November 15, 2024

MRI RSfMRI Protocol 1 - GE MR 750 Discovery (3T)													
Coil Selection: 32 Channel Head Coil  1. 3 Plane Localizer (2D FGRE)													
TR (ms)	TE (ms)	TI (ms)	FLIP ANGLE	FOV (cm)	FREQ MATRIX (mm)	PHASE MATRIX (mm)	SLICE THICKNESS (mm)	SLICE GAP (mm)	NEX	BANDWIDTH (kHz)	FREQ DIRECTION	ASSET	0:08
5	1.4	N/A	30	24	256	128	10	0	1	31.2	Unswap	N/A	
2. Calibr	ation Sca	ın (3D FS	PGR)										
													0:06
3. Sagitta	al T1 (3D	IR-FSPC	GR)										

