# **6.3. Pulmonary Function Tests**

Full pulmonary function tests including spirometry (Appendix I), plethysmography, and DLCO (Appendix II) will be performed according to ATS guidelines. MedGraphics Elite Series, MedGraphics Corporation. St. Paul, MN USA and/or nDD EasyOne Spirometer,

DATE: November 15, 2024

nDD Medical Technologies Inc. Andover, MA USA will be used. All measurements will be performed in the Pulmonary Function Laboratory at Robarts Research Institute.

LCI will be performed using the nDD Easy-One Pro Lab. Participants breathe normally into a mouthpiece connected to the device for 3-5 minutes.

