For participants undergoing fMRI, we will utilize an unpaired two tailed t-test to assess the differences of BOLD and DTI signal intensity between asthma underperceivers and healthy controls. Furthermore, we will assess Pearson correlations for fMRI measurements (BOLD signals and DTI data) with lung MRI and spirometry measurements. Spearman correlations will be used to analyze the relationship between fMRI measurements and Asthma Control Questionnaire (ACQ) scores. Significant differences in Pearson and Spearman correlations will be determined using 95% CI.

For healthy volunteers and asthmatic underperceivers undergoing fMRI, we will utilize a paired two tailed t-test to assess the within group differences of BOLD and DTI signal intensity before and after a methacholine challenge. Pearson correlations will be used to assess the relationship between quantitative fMRI data and spirometry measurements. Significant differences in Pearson correlations will be determined using 95% CI.

To demonstrate if differences exist in BOLD and DTI signal between asthmatics and healthy volunteers post methacholine challenge, we will utilize an unpaired two tailed t-test. Pearson correlations will be used to assess the relationship between quantitative fMRI data and spirometry measurements. Significant differences in Pearson correlations will be determined using 95% CI.

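### Section 4.1.1 makes salbutamol the next step after the gas scan and omits the post-methacholine fMRI, so the induced condition is not protected in participants scanned lung-first

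*Protocol*

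**What the plan says.** Section 4.1.1 has the only rule that times salbutamol at the challenge. After the dyspnea score and the helium or xenon scan at PC20, 400 µg "of Salbutamol (4 puffs) will be administered followed by spirometry 20 minutes post-administration". The fMRI is not named there. The same section limits the methacholine challenge to the baseline visit.

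Section 4.1.2 gives healthy volunteers and asthma underperceivers two fMRI sessions at that visit: "The sessions will be performed before and after the methacholine challenge for baseline and induced asthma attack or dyspnea conditions, respectively". Brain and lung imaging are to be done "within five minutes of each other at both baseline and post-methacholine, and the order in which they are performed will be randomized", and each participant keeps the same order at both time points.

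The synopsis repeats the fMRI before and after methacholine and the random order. Its methacholine paragraph mentions salbutamol rescue. Neither passage times salbutamol against the fMRI.

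The second fMRI feeds a hypothesis in section 3, "Healthy volunteers and asthma underperceivers will show significant differences in BOLD contrast after undertaking a Methacholine challenge", and two analyses in section 8: a "paired two tailed t-test to assess the within group differences of BOLD and DTI signal intensity before and after a methacholine challenge", and an unpaired test "To demonstrate if differences exist in BOLD and DTI signal between asthmatics and healthy volunteers post methacholine challenge".

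**The concern.** The two sections fit together in one scan order only. In a brain-first participant the fMRI is finished before the gas scan, so the scheduled dose cannot precede it. In a lung-first participant both conditions that 4.1.1 sets for the dose are met before the required fMRI begins. Staff who follow 4.1.1 step by step could give the bronchodilator and then acquire a scan that 4.1.2 wants in the induced condition.

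The section 8 t-tests treat every post-challenge scan as the same state. If any lung-first fMRI followed salbutamol, scans in two drug states would be pooled and drug state would be tied to scan order. Section 8 also correlates fMRI with lung MRI. In such a participant the lung image would be at PC20 and the post-challenge fMRI after the bronchodilator.

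This is a procedural matter. An analysis plan could set such a scan aside but could not restore it, and because the challenge is done only at baseline, no later visit replaces it.

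**Working it through.** **Inputs (protocol section 4.1.2 unless stated).**
- fMRI sequence times: localizer 0:08, calibration 0:06, T1 4:38, resting-state BOLD 6:00, DTI 8:48.
- Gap between brain and lung imaging: 0:00 to 5:00.
- Lung session maximum: "MRI will be performed for up to a period of 30 minutes".
- Spirometry 20:00 after the dose (4.1.1). For its location, section 6.3 says "All measurements will be performed in the Pulmonary Function Laboratory at Robarts Research Institute".
- Assumptions: no set-up time is counted, and the gas scan ends when the lung session ends.

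**Step 1. Reproduce the stated total.** 0:08 + 0:06 + 4:38 + 6:00 + 8:48 = 19:40, which matches the table.

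**Step 2. Lung-first timeline, with the end of the gas scan as 0:00.**
- BOLD starts 0:08 + 0:06 + 4:38 = 4:52 into the brain session. Adding the 0:00 to 5:00 gap gives 4:52 to 9:52.
- BOLD ends 6:00 later, at 10:52 to 15:52.
- DTI, and with it the session, ends 8:48 later, at 19:40 to 24:40.

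If salbutamol is given as the gas scan ends, the whole fMRI follows it.

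**Step 3. Does that schedule leave room for the spirometry?** The margin is 20:00 minus the end of the brain session:
- Gap 0:00: 20:00 − 19:40 = 0:20 after the session ends.
- Gap 5:00: 20:00 − 24:40 = −4:40, so spirometry falls 4:40 before the session ends.

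At best, 20 seconds remain to leave the scanner and reach the laboratory. Early dosing therefore hardly fits an exact 20 minutes. This favours the reading that salbutamol is held, but the protocol gives the 20 minutes no window, so the arithmetic does not settle it.

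**Step 4. Wait for salbutamol if it is held until both scans are done.**
- Either order, full lung session: 30:00 + (0:00 to 5:00) + 19:40 = 49:40 to 54:40 from the start of the first scan. Brain-first participants already wait this long.
- Extra wait in lung-first participants, against a dose at the end of the gas scan: (0:00 to 5:00) + 19:40 = 19:40 to 24:40.

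**Step 5. How many participants?** At most, the lung-first fMRI participants who reach PC20. The protocol plans 30 healthy volunteers but gives no number of underperceivers, no allocation ratio for scan order and no PC20 rate, so no count follows.

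**The case against.** The strongest reply is that 4.1.1 and 4.1.2 are compatible. Section 4.1.1 places the dose after the gas scan but does not say immediately after, so it can be read as an earliest time. Section 4.1.2 states the condition in which the second fMRI must be acquired. Holding salbutamol until both scans are done satisfies both sections, dosing before the fMRI defeats the stated purpose, and the spirometry arithmetic points the same way. On this view a visit worksheet can carry the step order.

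Much of this stands. A reader might infer from 4.1.1 that the protocol orders salbutamol before the fMRI in lung-first participants, or that their post-challenge scans are already lost. The text supports neither: it permits that sequence without requiring it, and the held reading is the more plausible one. A reader might also infer a dilution of the methacholine effect or a loss of power. The protocol gives no effect of salbutamol on BOLD or DTI, no allocation ratio and no effect size, so any such figure would rest wholly on assumptions.

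What does not stand is that the matter is already settled. The held reading has to be pieced together from a purpose clause, a sequence table and the location of the spirometer, while the one explicit instruction on salbutamol names only the dyspnea score and the gas scan. A written step order that works under one randomised order and not the other is more than absent detail.

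**Conclusion.** The point holds in a limited form and is a cheap improvement. Section 4.1.1 makes salbutamol the next step after the gas scan, omits the post-methacholine fMRI, and so does not protect the condition that 4.1.2 requires in lung-first participants. Brain-first participants are unaffected by the scheduled dose.

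No effect on any result has been shown. If the site already holds salbutamol until both scans are done, nobody is affected. No direction of bias, size of bias or power loss is claimed. The conclusion rests on the ordinary sense of 4.1.1 and on the absence of any other rule timing salbutamol against the fMRI. The timings rest on the listed sequence times, a gap of 0 to 5 minutes and no set-up time.

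**What to change.** Amend section 4.1.1 so that, in both scan orders, salbutamol is given once the dyspnea score, the gas MRI and, where applicable, the post-methacholine fMRI are complete, except for earlier clinical rescue. Spirometry follows 20 minutes after the dose.

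Record the clock times of salbutamol and of the BOLD start, and flag any fMRI acquired after salbutamol. Report the section 8 t-tests with and without the flagged scans. They should not simply be excluded: participants who need early rescue are plausibly those who responded most strongly, so dropping them would select on the response under study.

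The cost is one clause, two clock times at the baseline visit and one sentence of analysis. Compared with dosing at the end of the gas scan, lung-first participants wait about 20 to 25 minutes longer for salbutamol, which brings them level with brain-first participants. The rescue exception keeps clinical judgement ahead of the schedule. If salbutamol is already held in practice, the amendment only writes that down.

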#### 4.1.2. MRI

Participants will be screened for contraindications by the MR technologist. Prior to being made comfortable on the scanner bed in the magnet, participants will be required to do a 16-second breath-hold test using a dose bag containing air similar to that used for xenon imaging. This maneuver ascertains their ability at that time to undergo administration of Xe gas and a 16-second breath-hold for the MR study. They will be placed in the 3T MR scanner with one of three Xe chest coils fitted over their torso and chest. Hearing protection will be provided to each participant to muffle the noise produced by the gradient RF coils. A pulse oximeter lead will be attached to all of the participants to monitor their heart rate and oxygen saturation. MRI will be performed for up to a period of 30 minutes. All participants will have supplemental oxygen provided via nasal cannula at a flow-rate of 2 liters per minute during the scanning process.

Once comfortable on the MRI scanner table, participants will undergo 1 MRI session containing acquisition of several images as follows:

Proton (H) imaging – participants will inhale a 1 litre gas mixture containing medical grade nitrogen (N2). This is performed in order to match breath hold volumes and anatomy with Xe images. Breath hold will be up to 16 seconds.

Static ventilation imaging – participants will inhale a 1 litre gas mixture containing Xe and or He (5 ml/kg body weight) mixed with helium-4 (He) from a 1 litre bag. Breathhold will be up to 16 seconds.

Diffusion-weighted imaging – participants will inhale a 1 litre gas mixture containing Xe and or He (5 ml/kg body weight) mixed with He from a 1 litre bag. Breath-hold will be up to 16 seconds.

Dissolved phase imaging – participants will inhale a 1 litre gas mixture containing Xe mixed with He from a 1 litre bag. Breath-hold will be up to 16 seconds.

Logs and records of Xe and He gas exposure will be maintained for every participant in this study. Adverse experiences and pulse oximetry measurements during MRI will be recorded. If oxygen saturation falls to <80% continuously for ≥15 seconds, scanning will be discontinued, and the patient will be provided supplemental oxygen as necessary until oxygen saturation recovers to the patient's baseline value. This patient will then be discontinued from the study.

Participants undergoing resting state fMRI (healthy volunteers and the subset of asthmatic participants identified as underperceivers) will also be placed in the 3T MR scanner with a 32-channel brain coil fitted around their head. Hearing protection will be provided to each participant to muffle the noise produced by the gradient RF coils. A pulse

Protocol ROB0037, Robarts Research Institute Version 16

DATE: November 15, 2024

oximeter lead will be attached to all of the participants to monitor their heart rate and oxygen saturation. MRI will be performed for up to a period of 20 minutes. All participants will have supplemental oxygen provided via nasal cannula at a flow-rate of 2 liters per minute during the scanning process. Participants will undergo fMRI on two occasions during the first visit, each containing acquisition of an anatomical image, a BOLD signal image, and a diffusion tensor image. The sessions will be performed before and after the methacholine challenge for baseline and induced asthma attack or dyspnea conditions, respectively. Outlined in the table below are the appropriate pulse sequences designed for resting state fMR image acquisition:

Brain fMRI and lung MRI using Xe and/or He will be performed within five minutes of each other at both baseline and post-methacholine, and the order in which they are performed will be randomized for each participant and remain the same for both time points.

# Protocol ROB0037, Robarts Research Institute Version 16

DATE: November 15, 2024

MRI RSfMRI Protocol 1 - GE MR 750 Discovery (3T)													
Coil Selection: 32 Channel Head Coil  1. 3 Plane Localizer (2D FGRE)													
TR (ms)	TE (ms)	TI (ms)	FLIP ANGLE	FOV (cm)	FREQ MATRIX (mm)	PHASE MATRIX (mm)	SLICE THICKNESS (mm)	SLICE GAP (mm)	NEX	BANDWIDTH (kHz)	FREQ DIRECTION	ASSET	0:08
5	1.4	N/A	30	24	256	128	10	0	1	31.2	Unswap	N/A	
2. Calibr	ation Sca	ın (3D FS	PGR)										
													0:06
3. Sagitta	al T1 (3D	IR-FSPC	GR)										
TR (ms)	TE (ms)	TI (ms)	FLIP ANGLE	FOV (cm)	FREQ MATRIX (mm)	PHASE MATRIX (mm)	SLICE THICKNESS (mm)	SLICE GAP (mm)	NEX	BANDWIDTH (kHz)	FREQ DIRECTION	ASSET	4:38
7.4	3.1	400	11	25.6	256	256	1	0	1	31.25	S/I	2	
4. Axial	rsFMRI (	Single Sh	ot Multi-Ph	ase EPI-0	GRE)								
TR (ms)	TE (ms)	TI (ms)	FLIP ANGLE	FOV (cm)	FREQ MATRIX (mm)	PHASE MATRIX (mm)	SLICE THICKNESS (mm)	SLICE GAP (mm)	NEX	BANDWIDTH (kHz)	FREQ DIRECTION	ASSET	6:00
2500	25	N/A	90	22.4	64	64	3	0.3	1	250	R/L	2	
5. Axial	DTI (Sing	gle Shot E	EPI-SE)										
TR (ms)	TE (ms)	TI (ms)	FLIP ANGLE	FOV (cm)	FREQ MATRIX (mm)	PHASE MATRIX (mm)	SLICE THICKNESS (mm)	SLICE GAP (mm)	NEX	BANDWIDTH (kHz)	FREQ DIRECTION	ASSET	8:48
11000	58.3	N/A	90	24	96	96	2.5	0	1	250	R/L	2	
DIFFU TYI			OF CTIONS	# OF T	 IMAGES								
Ten	sor		41		6								
TOTAL (min:sec													19:40

# 4.1.3. Pulmonary Function Tests

Full pulmonary function tests including spirometry (Appendix I), plethysmography and diffusing capacity of carbon monoxide (DL $_{\rm CO}$ ) (Appendix II) will be performed on all participants according to ATS guidelines. MedGraphics Elite Series, MedGraphics Corporation. St. Paul, MN USA and/or nDD EasyOne Spirometer, nDD Medical Technologies Inc. Andover, MA USA will be used. All measurements will be performed in the Pulmonary Function Laboratory at Robarts Research Institute. Lung clearance index (LCI) is a marker of overall ventilation inhomogeneity within the lung derived from the multiple breath nitrogen washout (MBNW) test (Appendix III). Participants breathe normally into a mouthpiece connected to a device, the NDD EasyOne Pro Lab for approximately 3-5 minutes.

# 4.1.4. Forced Oscillation Technique (FOT)

FOT (Appendix IV) will be performed on all participants at each visit using the "tremoFlo™" Airwave Oscillometry System (THORASYS Thoracic Medical Systems, Montreal, QC). FOT is a method for measuring lung function without patient effort. FOT functions by superimposing a gentle multi-frequency airwave onto the patient's normal respiratory airflow while measures of airway impedance are acquired through the analysis of resulting pressure and flow signals. Participants breathe naturally throughout the measurement sequence, which comprises of at least 3 measurements of 16 seconds

DATE: November 15, 2024

each. Airwaves comprise of small amplitude pressure oscillations (<2 cm H2O peak to peak) well below the acceptable limits of 5 cmH2O, which are far below attainable physiological normal transpulmonary pressures. Airwaves are specifically designed for performance with carefully selected frequencies between 5 and 38 Hz, with a commonly used waveform including of 6, 11 and 19 Hz. These are experienced by the participants as very small flutters during breathing and are easily tolerated. Device verification will be conducted on each day of use to confirm calibration parameters and performance characteristics fall within expected values for a reference load.

